**Safety Evaluations:**

The safety population will consist of all subjects who are infused the study drug and have at least one post-dose safety assessment. Safety will be assessed by physical examinations, vital signs, electrocardiograms, AEs monitoring. AEs are graded per Guidance for Industry *Toxicity Grading Scale for Healthy Adult and Adolescent Volunteers Enrolled in Preventive Vaccine Clinical Trials*.

**Efficacy Evaluations:**

The parameters including, but not limited to, serum albumin level, colloid osmotic pressure, blood pressure, 24-hour fluid input and urine output, and body weight will be measured at baseline and at time points listed in [Table 1](#). The changes in serum albumin level, colloid osmotic pressure, blood pressure, body weight and other parameters will be assessed.

[figure not shown]
**Immunogenicity:** Blood samples for immunogenicity will be collected until 30 days after the infusion

**Statistical Analysis:** All PK, immunogenicity, safety and efficacy data will be summarized using descriptive statistics (number of subjects, mean, median, standard deviation, minimum, and maximum) for continuous variables and using frequencies and percentages for discrete variables.

## 1.2 Study Design Schema

Figure 1

### OsrHSA Phase 1 study design schema

### 1.3 Schedule of Activities

- a. Screening procedures will be performed at screening visits from D-28 to D-2, including ultrasound, smoking, alcohol, drug use test, serum albumin. Pre-dose from D-1 to infusion, smoking, alcohol, drug use test, serum albumin will be performed again. (The two times serum albumin average will be used as subject's baseline serum albumin)
- b. Urine collection will be performed 24hr after infusion
- c. The 0.5h time point after dose initiation will change to  $\pm 5$  minute window (instead of  $\pm 2$  minute).
- d. The D3 and D5 time points will change to  $\pm 6$  hour window (instead of  $\pm 4$ h)
- e. Abdominal ultrasound exam will be performed and reviewed during the 28 day screening period, prior to patient check-in on Day -1
- f. Alcohol and Cotinine will be tested at all follow-up visits (D3, D5, D8, D15, D22, D30)
- g. Syphilis will be tested at the screening timepoint, in order to adhere to the new exclusion criteria described above
- h. Anti-HCP antibody will be measured at the same time points as ADA
- i. In order to calculate accurate creatinine clearance, subjects' body weight will be re-measured at Day 8 and Day 30 visits.
- j.

Table 1 Schedule of Activities

Protocol Activity	Clinical Research Unit (CRU) Confinement										Outpatient Visits					
	Screen -D28 to -D2	Pre-dose -D1 to dose	Dose initiation	0.5 h $\pm$ 5m after Dose initiation	1.0h $\pm$ 10m after Dose initiation	EOI+ 10m	0.5h Post EOI $\pm$ 10m	4h $\pm$ 10m	12h $\pm$ 10m	D2 24h $\pm$ 30m	D3 $\pm$ 6h	D5 $\pm$ 6h	D8 $\pm$ 1d	D15 $\pm$ 2d	D22 $\pm$ 2d	D30 $\pm$ 2d
Signed Informed Consent (ICF) 	×															
Inclusion/Exclusion Criteria	×	×														

Protocol Activity	Clinical Research Unit (CRU) Confinement										Outpatient Visits					
	Screen -D28 to -D2	Pre-dose -D1 to dose	Dose initiation	0.5 h ± 5m after Dose initiation	1.0h ± 10m after Dose initiation	EOI+ 10m	0.5h Post EOI ± 10m	4h ± 10m	12h ± 10m	D2 24h ± 30m	D3 ± 6h	D5 ± 6h	D8 ± 1d	D15 ± 2d	D22 ± 2d	D30 ± 2d
Demographics 	×															
Weight 	×	×							×	×		×				×
Medical History 	×	×								×	×	×	×	×	×	×
Physical Examination 	×	×				×	×	×	×	×	×	×	×	×	×	×
Current Medications/OTC/supplements	×	×											×			×
Vital Signs 	×	×		×	×	×	×	×	×	×	×	×	×	×	×	×
12 Lead Electrocardiogram (ECG) 	×	×			×	×	×	×	×	×	×	×	×	×	×	×
Abdominal Ultrasound 	×															
Adverse Events (AE)	Ongoing															
Laboratory Tests																
Urine Drug Screen	×	×														
Alcohol Breath Test	×	×									×	×	×	×	×	×
Urine Cotinine Test	×	×									×	×	×	×	×	×
Pregnancy Test for Female 	×	×												×		×
Ig E and Ig G Against Rice	×							×			×	×		×		×
Hematology & Serum Chemistry 	×	×					×		×			×				×
Coagulation Tests	×											×				
Screening for HIV, HBV, HCV, Syphilis 	×															
Urine Analysis (U/A) 	×						×	×	×	×	×	×	×	×	×	×
Study Drug Administration			×													
Injection Site Reaction		×		×		×	×		×	×						
Pharmacokinetics (PK) 		×		×		×	×	×	×	×	×	×	×	×	×	×
Colloid Osmotic Pressure 		×		×		×	×	×	×	×	×	×	×	×	×	×
Anti-Drug Antibodies (ADA); Anti-HCP antibody 		×										×	×	×	×	×

**Abbreviations:** ADA = anti-drug antibody; EOI=End of Infusion; EOS=End of Study; EOT=End of Treatment; ECOG = Eastern Cooperative Oncology Group; ConMeds = Concomitant medications; CT = computed tomography; MRI = magnetic resonance imaging; HIV = human immunodeficiency virus; HBV = hepatitis B virus; HCV = hepatitis C virus; PD = pharmacodynamics; PK = pharmacokinetics

1. Written consent must be obtained prior to performing any protocol specific procedure.
2. Age, height, gender, ethnicity, and race at screening where possible.
3. Body weight will be measured at screening, predose and postdose at Day 2, D 3, Day 8 and Day 30 visits .. 24-hour liquid input (drinking water) and output (urine) will be recorded post EOI
4. Medical History: includes any significant or relevant diseases, surgeries, or other medical events during the past 5 years and any new conditions arising while enrolled in the study.
5. PE: Full physical examination including the cardiovascular, pulmonary, GI, and nerve system, and skin will be performed at screening and EOS visits, and partial physical examination can be done at other visits to assess any abnormalities or change from baseline, including focused skin and cardiopulmonary examination.
6. Vital signs include temperature, pulse, respiratory rate, and blood pressure. Vital signs will be assessed at screening and on the visits at the clinical research unit. Vital sign will be performed within 30 minutes prior to the infusion, at the EOI (+ 5 minutes) and before every PK sampling. Additionally, blood pressure will be measured every 10 minutes during infusion, every 30 min post EOI up to 6 hours, every 1 hour after 6 hours up to 12 hours post EOI, and every 2 hours until 24 hours post EOI or discharge, and at every outpatient visit. Blood pressure should be measured prior to Colloid osmotic pressure sampling when blood pressure measuring and colloid osmotic pressure sampling are specified to be done at the same time.
7. ECGs (12 lead) will be collected at screening, predose, during infusion(1hr),and EOI, prior to PK sampling during Day 1, and as clinically indicated, and at EOS.
8. Abdominal ultrasound exam will be performed and reviewed during the 28 day screening period, prior to patient check-in on Day -1
9. Only in women of childbearing potential. Urine pregnancy test will be done at screening and EOS, serum pregnancy test will be done pre-dose and on D15, or as clinically indicated.
10. Hematology includes Complete blood count (CBC) (hematocrit (HCT), hemoglobin, red blood cells (RBC), Red Cell Distribution Width (RDW), Mean Corpuscular Volume (MCV), Mean Corpuscular Hemoglobin (MCH), Mean Corpuscular Hemoglobin Concentration (MCHC), platelets, white blood cells (WBC) with absolute differential counts of neutrophils, lymphocytes, monocytes, eosinophils, and basophils). Serum Chemistry ALT, AST, ALP, K+, Na+, Cl-, Ca2+, TBIL, blood urea nitrogen (BUN) or urea, creatinine, uric acid, glucose (non-fasted).
11. HIV screening (Antigen/antibody test), HCV antibodies, hepatitis B surface antigen (HBsAg), hepatitis B surface antibody (anti-HBs), total hepatitis B core antibody (anti-HBc), IgM antibody to hepatitis B core antigen (IgM anti-HBc), Syphilis.
12. Twenty-four hours urine for D1 after the administration will be collected for 24 hours urine protein. Dipstick is acceptable for other time points. Microscopic analyses if clinically indicated. If  $\geq 2+$  protein on urine dipstick, then collect spot urine sample to calculate urine protein to creatinine ratio (UPCR) or collect 24h urine.
13. PK samples (Serum albumin) will be collected at pre-dose, 0.5h after dose initiating, EOI, and 0.5h, 4h, 12h, 24h (Day 2), 48h (Day 3), Day 5, Day 8, Day 15, Day 22, and Day 30 post EOI. The exact/actual time to collect blood will be documented.
14. Colloid osmotic pressure will be measured within 30 min predose, every 30 min after dose initiating until EOI, EOI, every 1 hour up to 6 hours post EOI, every 2 hour after 6 hours up to 12 hours post EOI, and every 4 hours until 24 hours post EOI or discharge, 48h (D3), D5, D8, D15, D22, and D30 post EOI. Blood pressure should be measured prior to each colloid osmotic pressure sampling.
15. Blood samples for ADA and Anti-HCP antibody analyses will be collected at pre-dose, D8, D15, D22, and D30 post EOI.

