## **5 PATIENT POPULATION**

### **5.1 Number of Subjects and Description of Population**

This study will enroll up to 40 healthy male or female subjects, 8 subjects for each of 5 cohorts, 18-55 years old, or more subjects might be recruited based on emerging data from this study and ongoing China clinical trial. Subject Selection and Numbering:

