14. Subjects who test positive for Syphilis, Human immunodeficiency virus (HIV) positive will also be excluded from the study
15. Immunization with a live or attenuated vaccine is prohibited within 4 weeks prior to study drug administration. Seasonal influenza vaccines for injection are generally killed virus vaccines and are allowed; however, intranasal influenza vaccines (e.g., FluMist®) are live attenuated vaccines and are not allowed)
16. Positive Ig E and Ig G against rice at screening
17. History of significant alcohol abuse within one year prior to screening or regular use of alcohol within six months prior to the screening visit (more than fourteen units of alcohol per week [1 unit = 150 mL of wine, 360 mL of beer, or 45 mL of 40% alcohol]) or positive alcohol breath test at screening
18. History of significant drug abuse within one year prior to screening or use of soft drugs (such as marijuana) within 3 months prior to the screening visit or hard drugs (such as cocaine, phencyclidine [PCP], crack, opioid derivatives including heroin, and amphetamine derivatives) within 1 year prior to screening
19. Positive urine drug screen, cotinine test, or alcohol breath test at screening
20. Any reason which, in the opinion of the Qualified Investigator, would prevent the subject from participating in the study.

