### 7.3 Immunogenicity Evaluations

Blood samples for ADA analyses will be collected at pre-dose, D8, D15, D22, and D30 post EOI

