### **11.4.3 Immunogenicity Analysis**

All samples will first be analyzed for ADAs in a screening assay. Study samples with results below the screening cut-off will be reported as negative for ADAs. In the event of a positive result in the screening assay, samples will be analyzed in the confirmatory assay.

The incidence of ADA will be summarized for all subjects who received at least one administration of study drug. Impact of ADAs on PK, PD, and safety of the study drug will be evaluated, if applicable.

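### Rice IgE/IgG is drawn five times after dosing but not pre-dose, so its only pre-exposure value is the eligibility result, 2 to 28 days old at dosing

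*Combined protocol and SAP*

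**What the plan says.** **Sampling times.** In Section 1.3, Table 1, the row "Ig E and Ig G Against Rice" carries marks at screening, 4 h, D3, D5, D15 and D30. The screening column is headed "Screen -D28 to -D2". The pre-dose column is blank for this row. Note a lists what is repeated before the infusion, and rice antibody is not in the list: "Pre-dose from D-1 to infusion, smoking, alcohol, drug use test, serum albumin will be performed again".

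**Eligibility.** Section 5.3, criterion 16, excludes subjects with "Positive Ig E and Ig G against rice at screening".

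**The other antibody tests.** Table 1, note 15: "Blood samples for ADA and Anti-HCP antibody analyses will be collected at pre-dose, D8, D15, D22, and D30 post EOI". These assays have a pre-dose sample.

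**Analysis.** Section 7.3 names only ADA samples: "Blood samples for ADA analyses will be collected at pre-dose, D8, D15, D22, and D30 post EOI". Section 11.4.3 summarises only ADA: "The incidence of ADA will be summarized for all subjects who received at least one administration of study drug". Section 11.4.2 tabulates continuous safety data as observed values and, where appropriate, change from baseline. It does not say whether rice IgE/IgG is included or which sample would be its baseline.

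**The concern.** The product is made in rice seed, and Section 2.3.3 names host cell protein as the main impurity. Safety is the primary objective. Five post-dose draws make sense only if someone intends to compare them with a value from before exposure, and the schedule offers one such value.

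That value has two weaknesses. It can be four weeks old at dosing, with ordinary life in between. It is also the reading on which subjects were admitted. A volunteer whose usual level sits near the cut-off enters when the screening reading happens to fall on the negative side, and later readings tend to return to that volunteer's usual level. This is regression to the mean. It can look like sensitisation when nothing has happened, and a real conversion in a borderline subject cannot be told apart from it.

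**Working it through.** **1. Column positions.** The rice row has no footnote giving its times, so I split Table 1 into its 16 visit columns and tested the mapping on rows whose times are also stated in text.

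| Row | Marks found | Agrees with text? |
|---|---|---|
| PK | pre-dose, 0.5 h, EOI, 0.5 h post EOI, 4 h, 12 h, D2, D3, D5, D8, D15, D22, D30 | yes |
| Pregnancy test | screening, pre-dose, D15, D30 | yes |
| Alcohol test | screening, pre-dose, D3, D5, D8, D15, D22, D30 | yes |
| ADA/anti-HCP | pre-dose, D5, D8, D15, D22, D30 | yes, except that D5 is not in note 15 |
| Weight | screening, pre-dose, 12 h, D2, D5, D30 | no (note 3) |
| Rice IgE/IgG | screening, 4 h, D3, D5, D15, D30 | no text to compare |

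If the 4 h mark were one column out, it would become 0.5 h post EOI or 12 h. The pre-dose cell would still be blank.

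**2. Age of the only pre-exposure value.** Counting without a day 0, D-28 to D1 is 28 days and D-2 to D1 is 2 days. The longest span from screening to the D30 sample is 28 + 29 = 57 days. A pre-dose sample (D-1 to dose) would be at most about 1 day old.

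**3. Numbers of subjects.** Section 5.1 gives "8 subjects for each of 5 cohorts", allocated 6:2. That is 5 × 6 = 30 on OsrHSA and 5 × 2 = 10 on placebo.

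**4. Illustration of apparent conversion with no drug effect.** All inputs here are assumed. Let two readings on one subject be bivariate standard normal with correlation ρ, and put the cut-off c at the 95th percentile (c = 1.645). Then

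P(later positive | screen negative) = [0.95 − Φ₂(c, c; ρ)] / 0.95,

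and, if the pre-dose reading must be negative as well,

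P = [Φ₂ − Φ₃] / Φ₂,

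where Φ₂ and Φ₃ are the probabilities that two or three readings all fall below c.

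| ρ | Φ₂ | Φ₃ | Screen negative: P, × 30 | Screen and pre-dose negative: P, × 30 |
|---|---|---|---|---|
| 0.5 | 0.9122 | 0.8816 | 3.98%, 1.19 | 3.35%, 1.01 |
| 0.7 | 0.9196 | 0.8974 | 3.20%, 0.96 | 2.42%, 0.73 |
| 0.9 | 0.9319 | 0.9205 | 1.91%, 0.57 | 1.22%, 0.37 |
| 0.95 | 0.9371 | 0.9295 | 1.36%, 0.41 | 0.81%, 0.24 |

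These are per draw.

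**5. Wider assumptions.** I simulated a between-subject SD of 1 on the log scale, a within-subject SD of 0.2 to 0.5, and 5 to 20% of volunteers above the cut-off. With no drug effect, 1.9 to 14% of screen-negative subjects read positive at D15 or D30. Of those, 28 to 41% would already have read positive at a pre-dose sample.

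**6. What the placebo group can show.** If 0 of 10 placebo subjects convert, the one-sided 95% upper bound on the background rate is 1 − 0.05^(1/10) = 26%.

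**The case against.** **No such analysis is defined.** The documents contain no rice baseline, no definition of a rice seroconverter and no treatment-emergent rice-antibody analysis. The only stated use of the test is exclusion 16. A reader might infer that the plan judges treatment-emergent rice antibody against screening, but the text does not say so. What stands is narrower: anyone who reads the five post-dose results against a pre-exposure value has only screening to use.

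**Other safeguards exist.** Anti-HCP antibody is aimed at the main impurity and has a pre-dose sample. Regression to the mean acts equally on both randomised arms, so the comparison with placebo is not biased. Both points are fair. But anti-HCP is a separate assay whose isotype coverage is not stated, it was not the eligibility test, and ten placebo subjects give an imprecise background rate.

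**The 4 h draw.** A reader might conclude that this draw is wasted and should be removed. The documents do not support that. They state no purpose for it, and the view that no new antibody can exist by 4 h is general immunology, not something they say. The sample could also serve as a rough near-baseline. Section 6.2.4 gives 50 + 200 + 50 = 300 mL infused; against an assumed 3 L of plasma this is about 10% dilution. In the model of step 5, a 4 h reading so diluted would flag 23 to 31% of the false D15/D30 positives, against 28 to 41% for a pre-dose sample. It still follows exposure, so dilution and antigen binding can affect it, and a pre-dose sample avoids both.

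**Selection is uncertain.** Because exclusion 16 joins the two isotypes with the word and, it may admit a subject positive for only one. If so, subjects were not all selected to be negative. That does not remove the need for a pre-dose value, since such a subject could be positive before dosing.

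**Conclusion.** The point holds as a gap in the sampling schedule. Rice IgE/IgG has five post-dose readings and one pre-exposure reading, and that reading is 2 to 28 days old and doubles as the eligibility test. The companion antibody assays do not share this gap. It limits what the trial can say about rice sensitisation, and closing it costs little.

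The size is not established. A reader might take the percentages above as expected false-conversion rates, but they rest wholly on assumed variability and cut-offs, and the documents supply neither. They show only that roughly one apparent conversion among 30 active subjects is plausible without any drug effect. A pre-dose sample is also only a partial remedy: in the step 5 model, 59 to 72% of the spurious D15/D30 positives would remain. Its value is that it supplies a contemporaneous baseline on which nobody was selected.

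The blank pre-dose cell is read from a machine-extracted table, but the conclusion survives a one-column shift.

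**What to change.** - In Table 1, add a pre-dose tick for rice IgE/IgG, run on blood from the existing pre-dose ADA/anti-HCP draw, and add the test to the pre-dose list in note a. The result need not be available before dosing, since it serves only as baseline.
- In Section 11.4, state that post-dose rice IgE/IgG is reported by arm as change from the pre-dose sample. Keep the screening sample for eligibility only.
- Clarify whether exclusion 16 refers to either isotype or both.

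**Cost.** Up to 5 × 8 × 1 = 40 extra samples assayed and a small extra blood volume, with no added venepuncture. The sponsor may offset this by dropping the 4 h sample if it has no other purpose, but the fix does not depend on that.

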Study Design:	
This is a Phase 1 randomized, double blinded, placebo-controlled, single dose escalation study to evaluate safety, tolerability, PK, and immunogenicity of OsrHSA in healthy volunteers (See study design schema).
 
After a screening period of up to 28 days, the qualified subjects will be randomized to OsrHSA or placebo (6:2). Each enrolled subject will receive one single assigned dose of OsrHSA or placebo. The investigator and subjects will be blinded to treatment assignment. During the study, subjects will be evaluated for safety and tolerability, PK/PD, and activity of OsrHSA.
 
On day 1, OsrHSA or placebo will be administered as single IV infusion at a rate lower than 2 ml/min to the subjects. Patients will be observed overnight. On Day 2, after completion of the study procedures and assessments, subjects will be discharged from the clinical research center. Seven-day dose-limiting toxicity (DLT) observational period will commence upon completion of dosing at the end of infusion (EOI). Subjects will have end-of-study (EOS) follow-up visits on Day 30 after infusion.
 
The planned doses are 20, 40, 80, 140, and 200 mg/kg, dose level(s) higher than 200mg/kg might be an option(s) based on emerging data from this study and ongoing China clinical trial (China IND#: CXSL1500135; Protocol Number: HY1001) .

Dose escalation decisions will be determined based on toxicities data as well as available all available PK data observed within 7 days after dosing.

**Study participation  
Duration:**

The screening period is up to 28 days, one treatment day, and follow-up period of 30 days

**Pharmacokinetic (PK)  
evaluations:**

Blood samples for single dose PK will be collected from all subjects to determine the albumin concentration changes, they will be taken at time points listed in [Table 1](#). The PK of OsrHSA will be analyzed using standard non-compartmental analysis (NCA) by validated software WinNonLin version 6.4 or higher (Certara, NJ, USA). PK parameters derived from NCA analysis will include, but not limit to,  $AUC_{0-\infty}$  and  $AUC_{0-t}$ ,  $C_{max}$ ,  $t_{1/2}$ , CL, and  $V_d$ . PK parameters will be listed for each subject and summarized with descriptive statistics by each dose level/cohort. PK parameters will also be presented with baseline corrected.

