#### 4.2.1 Definition of Dose Limiting Toxicity (DLT):

AEs will be graded according to the FDA Guidance for Industry *Toxicity Grading Scale for Healthy Adult and Adolescent Volunteers Enrolled in Preventive Vaccine Clinical Trials*. DLT is

defined according to the criteria below as any TEAEs occurring during the DLT observation period (7 days) and considered to be related to OsrHSA:

*Any Grade  $\geq$  3 AE or laboratory abnormality as defined in the FDA Guidance for Industry Toxicity Grading Scale for Healthy Adult and Adolescent Volunteers Enrolled in Preventive Vaccine Clinical Trials*

All Grade 3 toxicities for vital signs and laboratory parameters must be confirmed with a repeat measurement obtained within 1 hour or as soon as possible for vital signs and within 24 hours for laboratory parameters.

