#### **4.2.2 Dose-escalation Criteria:**

Tolerability and safety of subjects in a cohort will be reviewed by the SRC which is comprised of an independent Medical Monitor, site Principal Investigator, and Sponsor Study Director. Dose escalation may be stopped at any time based upon the Sponsor or Investigator's clinical assessment or judgment. Upon completion of the DLT observational period (first week after dosing), the SRC will examine safety data through Week 1 for each dose cohort in combination with all available, previously accumulated safety data, as well as available PK data, if any, from all subjects enrolled in the study to date. All cohorts will enroll 8 subjects (safety data from at least 6 or 7 subjects would be needed for SRC meeting, in case a subject discontinues the study), if no more than 2 out of 8 subjects experiences DLT as defined in the section 4.2.1, dose will be escalated to the next dose level.

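### Table 1 schedules no hematology, chemistry or coagulation test in the last 72 h of the 7-day DLT window, and it contradicts note i and footnote 3 on Day 8

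*Combined protocol and SAP*

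**What the plan says.** **DLT window.** The synopsis (section 1.1) states: "Seven-day dose-limiting toxicity (DLT) observational period will commence upon completion of dosing at the end of infusion (EOI"). Section 4.2.1 limits DLTs to events "occurring during the DLT observation period (7 days) and considered to be related to OsrHSA" and includes any Grade 3 or higher "AE or laboratory abnormality as defined in the FDA Guidance for Industry".

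**Decision.** Under section 4.2.2, once that period is complete, "the SRC will examine safety data through Week 1 for each dose cohort", together with accumulated earlier data. Escalation then turns on the number of subjects with a DLT.

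**Blood safety labs.** In Table 1 (section 1.3), "Hematology & Serum Chemistry" is marked at screening, pre-dose, 0.5 h post EOI, 12 h, D5 and D30. Coagulation is marked at screening and D5. Footnote 10 lists the analytes, creatinine among them, but gives no times. Section 7 gives no safety-lab times either, so the table row is the site's only instruction.

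**Weight and creatinine clearance.** Note i, above Table 1, says that for an accurate creatinine clearance "body weight will be re-measured at Day 8 and Day 30 visits". Footnote 3 puts post-dose weights at Days 2, 3, 8 and 30. The Table 1 weight row is marked post-dose at 12 h, D2, D5 and D30.

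**The concern.** The DLT definition and the SRC review both span a full week, but the blood tests that would reveal a hematology, chemistry or coagulation DLT stop at D5. A change without symptoms in transaminases, creatinine or cell counts that first appeared after D5 would have no scheduled test before the SRC decides. The subject would then be counted as free of a DLT over seven days on blood data covering about four.

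The 24-hour repeat rule in section 4.2.1 does not close the gap, because it applies only after an abnormal value has been found.

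Note i sharpens the question. It assumes that creatinine clearance is calculated at Day 8, but Table 1 provides neither of the two measurements for that day. The site therefore holds instructions that cannot all be followed.

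**Working it through.** **1. Day convention.** Footnote 13 equates 24 h with Day 2 and 48 h with Day 3 post EOI. So hours = (day − 1) × 24. Check: (2 − 1) × 24 = 24 and (3 − 1) × 24 = 48, as stated. Hence D5 = 96 h and D8 = 168 h.

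**2. Window.** 7 × 24 = 168 h from EOI, so it closes at nominal D8.

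**3. Time without a scheduled blood panel** = 168 − time of the last panel before the window closes.

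| D5 draw | Time | Gap | Share of window |
|---|---|---|---|
| 6 h early | 90 h | 78 h | 78/168 = 46% |
| Nominal | 96 h | 72 h | 72/168 = 43% |
| 6 h late | 102 h | 66 h | 66/168 = 39% |

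If Week 1 is read as calendar Days 1 to 7, the remainder is 7 − 5 = 2 days (D6 and D7). Urinalysis is marked at D8, so its nominal gap is 0 h.

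**4. If a blood panel fell at D8.** The nominal gap would be 168 − 168 = 0 h. The D8 visit window of ±1 day spans 144 to 192 h. An early draw would leave up to 24 h uncovered, and a late one would fall up to 24 h after the window closes.

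**5. Table 1 rows against their notes (post-dose times).**

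| Row | Table 1 | Note or footnote | Agreement |
|---|---|---|---|
| Weight | 12 h, D2, D5, D30 | Footnote 3: D2, D3, D8, D30; note i: D8, D30 | No |
| Creatinine (chemistry) | 0.5 h post EOI, 12 h, D5, D30 | Note i implies D8, D30 | Not at D8 |
| ADA | D5, D8, D15, D22, D30 | Footnote 15 and section 7.3: D8, D15, D22, D30 | Extra D5 mark |
| PK | 12 post-dose marks | Footnote 13: the same 12 | Yes |
| Pregnancy | D15, D30 | Footnote 9: D15, EOS | Yes |
| Alcohol, cotinine | D3, D5, D8, D15, D22, D30 | Note f: the same | Yes |

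Note i names weight, not creatinine. The need for a Day 8 creatinine follows from the purpose it states: the Cockcroft-Gault equation, named in inclusion criterion 5, uses both.

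**6. Is the D5 mark an effect of text extraction?** The weight, hematology/chemistry, coagulation, PK, pregnancy and ADA rows each have exactly 16 cells for the 16 visit columns. In the weight and chemistry rows the D30 mark sits correctly in the last column, whereas a dropped cell would have moved it too. A shift also cannot add a mark, and the ADA row has one more than its footnote. An artefact is therefore less likely, but it is not excluded.

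**The case against.** The strongest objection is that the D5 mark may simply be wrong. The first three post-dose weight marks (12 h, D2, D5) sit one column to the left of footnote 3 (D2, D3, D8), so D5 stands where D8 belongs. If the chemistry mark was likewise meant for D8, note i is satisfied and the DLT gap disappears. This stands as a real possibility that only the source table can settle. It would still leave a wrong schedule in the site's hands, unless the source table already shows D8.

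It can also be said that several lettered notes read like descriptions of changes. Note i nevertheless states a current requirement, and footnote 3, which belongs to the table itself, repeats the Day 8 weight. Notes c, d, f, g and h are all reflected in Table 1; note i is not.

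Three stronger inferences are not supported by the documents:

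- *That all laboratory DLTs go unobserved after D5.* Urinalysis, vital signs, ECG and physical examination are marked at D8 (footnote 7 does not list that ECG), adverse-event collection is ongoing, and any of these could prompt unscheduled blood tests.
- *That every Grade 3 laboratory value in the week is a DLT.* Section 4.2.1 also requires that it be considered related to OsrHSA.
- *That the protocol breaks its own rule by having no last-day panel.* Sections 4.2.1 and 4.2.2 set a window and a review period. Neither requires a panel on the final day, and D5 lies within the window.

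**Conclusion.** The point holds for scheduled hematology, chemistry and coagulation. As Table 1 reads, none of these is drawn in the last 72 h of the 168 h DLT window (43%; 66 to 78 h, or 39 to 46%, with the D5 visit window), while the DLT definition and the SRC review are worded for the whole week. This rests on the window starting at EOI, on the footnote 13 day convention, and on the table marks being as they appear in the extracted text.

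Separately, Table 1 contradicts note i and footnote 3 on Day 8 weight and provides no creatinine for the Day 8 clearance that note i implies. If the source table has the same marks, this inconsistency needs correcting whether D5 was intended or is a misplaced mark. If the source table already shows D8 in the chemistry, coagulation and weight rows, both parts fall away.

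The documents do not show how many laboratory events would be missed, so no effect on escalation decisions can be quantified.

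**What to change.** Check the source of Table 1. Reconcile the hematology/chemistry, coagulation and weight rows with note i, footnote 3 and sections 4.2.1 and 4.2.2, and the ADA row with footnote 15 and section 7.3. The aim is that scheduled blood labs and the stated 7-day laboratory DLT window agree before the SRC decides. Two routes achieve this:

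- The blood schedule covers the window. Blood is already drawn at D8 for PK, colloid osmotic pressure and ADA, so the cost is about one extra tube per subject at an existing draw (more if panels need separate tubes). Because of the ±1 day visit window, the text should also say how draws before or after 168 h count.
- The schedule stays as it is, and sections 4.2.1 and 4.2.2 state that hematology, chemistry and coagulation DLTs are assessed only up to the last scheduled panel. This costs only wording, but note i and footnote 3 must still be reconciled with the table.

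The choice is for the sponsor and investigator. No change to dose, DLT grade or stopping rules is implied.
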